Envarsus XR in African American Renal Transplant Recipients

NCT Number: NCT02956005

Date: 07/25/2016

Study Protocol

Title: Envarsus XR in African American Renal Transplant Recipients

Introduction

Tacrolimus is overwhelmingly used as an immunosuppressant in kidney transplantation, both early posttransplantation and as part of long-term maintenance regimens. While highly effective in preventing acute transplant rejection, tacrolimus has several limitations, including a narrow therapeutic window (necessitating drug monitoring and individual dose titration), interindividual variation in absorption, and low bioavailability of the currently widely used immediate-release tacrolimus (IR-Tac) twice-daily capsule formulation (Prograf; Astellas Pharma US, Inc).¹ In addition, both the IR-Tac formulation and another extended-release once-daily tacrolimus formulation (Advagraf/Astagraf XL; Astellas Pharma US, Inc) are associated with similar peak concentrations²; unwanted tacrolimus-associated neurologic adverse events (AEs) have been noted to happen or be most pronounced at peak serum tacrolimus blood concentrations. Additionally, the twice-daily formulation adds further pill burden to a patient population already encumbered with taking many long-term medications. Multiple daily drug dosing is associated with increased risk for nonadherence; this may result in acute rejection and, in severe cases, transplant failure.

The medication LCP-Tacro (LCPT; Envarsus XR; Veloxis Pharmaceuticals) is an extended-release tablet formulation of tacrolimus with once-daily dosing that has been developed using a proprietary MeltDose drug delivery technology (Veloxis Pharmaceuticals), distinguishing LCPT from other once-daily extended-release tacrolimus

products (eg, Astagraf XL). The MeltDose technology decreases a drug's particle size to the smallest possible units as single molecules. Drug particle size critically affects drug dissolution and absorption; if particle size is smaller, the surface area of the drug increases and the drug will be dissolved more quickly, resulting in better absorption. Results of the MeltDose technology are increased absorption and bioavailability associated with LCPT tablets compared with other extended-release and IR tacrolimus formulations currently available. Phase 1 and phase 2 trials confirmed that LCPT enables broader absorption throughout the gastrointestinal tract and sustains consistent tacrolimus concentrations⁴. In addition, LCPT showed a lack of diurnal variability common with other formulations.

Phase 2 trials of de novo and stable kidney and liver recipients showed a steadier and more consistent concentration-time profile over 24 hours, with reduced peak and peak-to-trough fluctuations for LCPT compared to IR-Tac, increased bioavailability of ~30%, and comparable efficacy and safety profiles. A robust correlation between the area under the curve at 24 hours and the minimum concentration was also shown, indicating that therapeutic drug monitoring of minimum concentration as a measure of tacrolimus exposure can be applied to LCPT. A phase 3 conversion trial showed that LCPT had noninferior efficacy and comparable safety profile to IR-Tac, with lower doses (~20% lower than IR-Tac overall and 30% lower in white patients) of LCPT⁵.

Hypothesis

African American renal transplant recipients that receive Envarsus will have less tubular injury and calcineurin inhibitor toxicity compared with patients that receive tacrolimus IR.

Study Type/Design

This is a case control study where a prospective cohort will be started de novo on Envarsus at the time of renal transplantation.

Endpoints

Primary endpoint is to determine the rate of calcineurin inhibitor toxicity as measured by surveillance kidney biopsies.

Secondary endpoint is to determine the rate of development of donor specific antibodies of the patients treated with Envarsus vs the patients treated with immediate release tacrolimus.

Patient Recruitment

We will prospectively consent 100 African American patients that will be receiving kidney transplants at our center. This cohort will be matched with a retrospective cohort of African American renal transplant recipients who received renal transplant and were treated with immediate release tacrolimus.

Exclusion criteria will include patients that are not African American and patients that are younger than 18 years old.

Inclusion Criteria

1. African American race

2. Adult renal transplant recipients (≥ 18 y/o)
3. Previous adverse reaction or contraindication to the use of tacrolimus

Exclusion Criteria

1. Non African American race
2. Less than 18 y/o (pediatric patients)
3. Recipients of liver and small bowel transplants
4. Adverse reaction to tacrolimus

Statistical analysis:

Data will be analyzed using standard statistical methods using chi square test, students T-square test, kaplan-meyer curve. No statistical analysis has been performed to achieve adequate power as this an observational study.

Treatment Overview

Screening will be performed by the Principal Investigators during the kidney transplant evaluation clinics, during the wait list kidney transplant evaluation clinic and prior to a schedule kidney transplant surgery.

Dosage and Administration of Envarsus XR

Patients enrolled in the prospective arm of the study will be started on Envarsus XR at 0.17mg/kg. The dose will be targeted to achieve a tacrolimus level between 8-10 ng/mL.

The tacrolimus level will be modified depending on the results of the surveillance biopsy, BK and CMV viruses, and donor specific antibody studies.

Laboratory Testing and Study Schedule

Schematic diagram of data that will be obtained during study:

Data to be obtained at time 0 on the prospective and retrospective cohort

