1. BMI

2. Weight
3. Sex
4. Reason for chronic kidney disease
5. Induction agent
6. Crossmatch results
7. Type of donor
8. Donor age
9. Donor sex
10. Donor end creatinine
11. Donor's biopsy result if available

Data to be obtained at time 1 month, 3 month, 6 month and 12 month on the prospective and retrospective cohort

1. Creatinine level
2. Proteinuria
3. Tacrolimus level
4. Diabetes
5. Blood pressure
6. BK virus serum
7. CMV virus PCR
8. Donor specific antibody
9. Biopsy results (at 3 and 12 months surveillance and any other additional for cause biopsy that the patient may have had)

10. Infections
11. Hospital admissions
12. Blood transfusions (if any)

Patient Monitoring and Evaluation

Patients will have a kidney biopsy at time 0 (at the time of implantation and prior to reperfusion), 3 months and 12 months. If at any other time it is clinically necessary to perform another biopsy, it will be performed.

Potential Pitfalls and Contingencies

If a patient develops side effects that are attributed to tacrolimus, then the patient may have to be switched to another immunosuppression regimen.

References

1. Prograf [prescribing information]. Northbrook, IL: Astellas Pharma US, Inc; September 2013.

3. Bechstein WO. Neurotoxicity of calcineurin inhibitors: impact and clinical management. *Transpl Int.* 2000;13(5):313-26.

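### The secondary endpoint counts newly developed donor-specific antibody, but no antibody result is collected before transplant in either cohort

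*Combined protocol and SAP*

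**What the plan says.** The Endpoints section gives one secondary endpoint, which is to "determine the rate of development of donor specific antibodies of the patients treated with Envarsus vs the patients treated with immediate release tacrolimus". It does not define development further.

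Laboratory Testing and Study Schedule has two data lists, each covering both cohorts.

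- The first is headed "Data to be obtained at time 0 on the prospective and retrospective cohort". It has 11 items: BMI, weight, sex, cause of kidney disease, induction agent, crossmatch, donor type, donor age, donor sex, donor end creatinine and donor biopsy. The only one that bears on antibody is item 6, "Crossmatch results", with no method or threshold.
- The second is headed "Data to be obtained at time 1 month, 3 month, 6 month and 12 month on the prospective and retrospective cohort". Item 8 is "Donor specific antibody". The first scheduled DSA value is therefore at month 1.

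DSA is mentioned once more, under Dosage and Administration of Envarsus XR: "The tacrolimus level will be modified depending on the results of the surveillance biopsy, BK and CMV viruses, and donor specific antibody studies". No timing or pre-transplant sample is given there.

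The four exclusion criteria concern race, age, other organ transplants ("Recipients of liver and small bowel transplants") and adverse reaction to tacrolimus. On the comparator, Patient Recruitment says "This cohort will be matched with a retrospective cohort of African American renal transplant recipients", without the matching variables, the ratio or the cohort size. The Statistical analysis paragraph names tests and states that power was not calculated. It has no rule for patients who are already antibody-positive.

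**The concern.** An antibody present before the first dose cannot be an effect of tacrolimus formulation. To measure development, the analysis must know who was negative at the start, and the listed data do not show this.

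The damage depends on how preformed antibody is distributed:

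- **Equal share in both cohorts.** Counting it adds the same background to each side and dilutes a true difference.
- **Unequal shares.** A false difference can appear in either direction, or a true one can be hidden.

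One cohort is prospective and the other historical, there is no randomisation, and the matching variables are not stated. Balance in prior sensitisation is neither assured nor ruled out.

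**Working it through.** **Reading check.** Four places could separate new from preformed antibody, and none does.

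| Place | What it offers |
|---|---|
| Time-0 list | Crossmatch only; no DSA |
| Eligibility | Nothing on DSA, crossmatch or sensitisation |
| Matching | Variables not stated |
| Statistical analysis | No definition of new DSA; no rule for prior positives |

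Conversion from negative at month 1 to positive at month 3, 6 or 12 can be observed. The gap concerns antibody first seen at month 1.

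**Illustration of size.** The plan gives no DSA rate, alpha or power, so there is no figure to reproduce. From the documents: 100 patients in the prospective cohort. Assumed: 100 in the retrospective cohort, two-sided 5% test, and every rate below.

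Let f be the preformed share, s the share of preformed antibody still positive at follow-up, and q the new-DSA rate. If any positive is counted:

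observed rate = f·s + (1 − f·s)·q

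The chance of p<0.05 comes from a two-proportion z-test (pooled standard error under the null, unpooled under the alternative). The corrected column is the continuity-corrected chi-square by exact binomial enumeration.

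*False difference: q = 10% in both cohorts, no drug effect*

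| f in the two cohorts | s | Observed rates | Difference (points) | Chance of p<0.05 | Corrected |
|---|---|---|---|---|---|
| 5% vs 10% | 1 | 14.5% vs 19% | 4.5 | 13.6% | 9.5% |
| 5% vs 15% | 1 | 14.5% vs 23.5% | 9 | 36.7% | 30.0% |
| 5% vs 10% | 0.5 | 12.25% vs 14.5% | 2.25 | 7.5% | 4.5% |
| 5% vs 15% | 0.5 | 12.25% vs 16.75% | 4.5 | 14.7% | 10.0% |

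Worked line: f = 0.15, s = 1 gives 0.15 + 0.85 × 0.10 = 0.235. These chances should be read against the nominal 5%. If the cohort with 15% preformed has 50 or 200 patients instead of 100, the 36.7% becomes 28.8% or 44.1%.

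*Hidden difference:* with true rates of 10% and 20%, preformed shares of 15% and 5% and s = 1, the observed rates are 0.15 + 0.85 × 0.10 = 23.5% and 0.05 + 0.95 × 0.20 = 24%.

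*Dilution: true rates 20% vs 8%, same f in both cohorts.* Power with no preformed antibody is 68.9%.

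| f | Observed if counted, s = 1 | Power, s = 1 | Power, s = 0.5 | Power with time-0 positives excluded (n per cohort) |
|---|---|---|---|---|
| 5% | 24.0% vs 12.6% | 55.0% | 61.5% | 66.6% (95) |
| 10% | 28.0% vs 17.2% | 44.6% | 55.0% | 64.3% (90) |
| 15% | 32.0% vs 21.8% | 36.9% | 49.4% | 61.8% (85) |

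In every row, excluding time-0 positives loses patients but keeps more power than counting them.

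**The case against.** The strongest reply is that nothing in the plan tells the analyst to count preformed antibody. On its plain meaning, an antibody present before transplant has not developed. Crossmatch is recorded in both cohorts, and three of the four visits can show conversion in patients negative at month 1. That narrows the problem but does not close it. The right reading of the endpoint cannot be applied to a month-1 positive without an earlier DSA result. The plan does not say how crossmatch was done or that it will be used to classify, exclude or match patients. Month 1 is itself a post-treatment value.

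A second objection is that the size rests wholly on assumed rates. This stands. The 37% figure needs a threefold imbalance and full persistence, and nothing in the documents suggests either. At half persistence with 5% vs 10%, the corrected test gives 4.5%, not above the nominal level. The dilution figures also matter less in a plan that claims no power.

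Third, this is a secondary endpoint in an observational comparison whose hypothesis concerns tubular injury and calcineurin inhibitor toxicity, and imbalance in preformed antibody is one instance of the wider matching problem. That limits the importance of the point but does not answer it.

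The centre may hold pre-transplant DSA results on file. If so the remedy is nearly free, but the plan does not call for collecting them.

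**Conclusion.** The concern holds. With the data listed, an antibody first detected at month 1 cannot be reliably classed as new or preformed in either cohort, and no other provision of the plan makes up for this. Confidence in the omission is high.

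The size of the consequence is unknown. Across the assumed scenarios with no drug effect, the chance of a false significant difference runs from about the nominal 5% to about 37% with 100 per cohort. Power for an assumed 20% vs 8% falls from 69% to between 61% and 37%. These figures show what is possible and do not estimate what will happen. The sponsor should correct this, because it affects the only stated secondary endpoint; it does not undermine the study as a whole.

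**What to change.** 1. Add the pre-transplant DSA result, taken from existing records, to the time-0 list for both cohorts. Record the assay and positivity threshold, since historical and current practice may differ.
2. Define the main analysis as new DSA at any follow-up visit among patients DSA-negative at time 0. Report new specificities in time-0-positive patients separately.
3. For patients with no time-0 result, report as a sensitivity analysis only the conversions at month 3, 6 or 12 among those negative at month 1, stratified by crossmatch. State that this conditions on a post-treatment result and misses antibody arising in the first month. Strata may be sparse.
4. Report the number without a time-0 result by cohort. Unequal missingness could itself introduce selection bias.

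The cost is one record-based data item and a short endpoint definition, with no added visit or change to treatment. The main analysis loses patients: at 10% preformed, 90 instead of 100 per cohort. The documents do not say whether pre-transplant DSA records exist for the retrospective cohort. If many are missing, the main analysis shrinks further and the sensitivity analysis carries more weight.

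### Control eligibility does not ensure that the surveillance biopsies and scheduled antibody tests behind both endpoints were done in the retrospective cohort

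*Combined protocol and SAP*

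**What the plan says.** **Endpoints.** The primary endpoint is tied to one kind of biopsy: "Primary endpoint is to determine the rate of calcineurin inhibitor toxicity as measured by surveillance kidney biopsies". The secondary endpoint is explicitly comparative: "Secondary endpoint is to determine the rate of development of donor specific antibodies", with the two formulations set against each other.

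**Patient Recruitment.** The treated cohort is enrolled forward in time: "We will prospectively consent 100 African American patients that will be receiving kidney transplants at our center". The controls are not: "This cohort will be matched with a retrospective cohort of African American renal transplant recipients who received renal transplant". Their drug was immediate-release tacrolimus. No calendar period, number of controls, matching ratio or matching variables are given. The listed inclusion and exclusion criteria concern race, age, other organ transplants and tacrolimus reactions. None concerns biopsies or antibody tests.

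**Laboratory Testing and Study Schedule.** One list covers both cohorts: "Data to be obtained at time 1 month, 3 month, 6 month and 12 month on the prospective and retrospective cohort". It includes donor specific antibody, and a single biopsy item that holds the 3- and 12-month surveillance results together with any for-cause biopsy.

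**Patient Monitoring and Evaluation.** Biopsies are promised: "Patients will have a kidney biopsy at time 0 (at the time of implantation and prior to reperfusion), 3 months and 12 months".

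**Statistical analysis.** Chi-square, t test and Kaplan-Meier methods are named. There is no denominator for the biopsy rate, no rule for missing biopsies or antibody tests, and no statement on whether for-cause biopsies count towards the primary rate.

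**The concern.** A patient with no surveillance biopsy has no primary outcome, and a patient with no antibody test has no secondary one. In the prospective cohort the plan can make these tests happen. In the retrospective cohort it can only find the ones that were done. As written, a recipient transplanted before any surveillance programme began, or biopsied only because creatinine rose, is an eligible control.

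If testing in the control period was incomplete, the controls who were tested may not be typical of all controls. The two cohorts could then show different toxicity or antibody rates with no difference between the formulations. The 3- and 12-month biopsies and the antibody results carry the whole comparison, so at stake is whether a difference in either rate can be put down to the drug or to how closely each group was examined. The issue is whether a test took place, not how a slide was read.

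**Working it through.** **Step 1. What each cohort is assured of.**

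| Item | Prospective cohort | Retrospective cohort |
|---|---|---|
| Biopsy at 3 and 12 months | Undertaking to perform (Patient Monitoring and Evaluation) | The undertaking is in the future tense and cannot bind patients already treated |
| Antibody at months 1, 3, 6, 12 | On the data list, and can be carried out | On the data list, retrievable only if done |
| Eligibility tied to testing | Not needed | None |
| Calendar period | Enrolment onward | Not stated |
| Rule for absent results | None | None |

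Nothing in the documents says whether the centre ran the same biopsy and antibody schedule when the controls were transplanted.

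**Step 2. Is there a figure to reproduce?** No. The 100 is given without inputs, and the Statistical analysis section says that no power calculation was done.

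**Step 3. A hypothetical, to see what drives the bias.** Every input is an assumption: 100 patients per cohort (the number of controls is not stated); 20% true toxicity in both; all prospective patients biopsied; 60 or 30 controls with a surveillance biopsy. For row (d) only, half of the remaining controls have just a for-cause biopsy, with 40% toxicity on those. Of the 100 controls, 20 truly have toxicity and 80 do not.

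- (a) Surveillance biopsies only, receipt unrelated to toxicity: 60 × 0.20 = 12, and 12/60 = 20%. With 30: 6/30 = 20%.
- (b) Surveillance biopsies only, toxic patients twice as likely to have one: 20(2q) + 80q = 60 gives q = 0.5. All 20 toxic patients are biopsied, and 20/60 = 33.3%. With 30: q = 0.25, and 10/30 = 33.3%.
- (c) Surveillance biopsies only, toxic patients half as likely: 20(r/2) + 80r = 60 gives r = 0.667. Then 20 × 0.333 = 6.7, and 6.7/60 = 11.1%. With 30: r = 0.333, and 3.3/30 = 11.1%.
- (d) For-cause biopsies pooled in: (12 + 20 × 0.40)/80 = 20/80 = 25%. With 30: (6 + 35 × 0.40)/65 = 20/65 = 30.8%.
- (e) Unbiopsied controls counted as free of toxicity: 12/100 = 12%. With 30: 6/100 = 6%.

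Control rate minus the Envarsus rate of 20%, in percentage points (positive favours Envarsus):

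| Case | 60 of 100 biopsied | 30 of 100 biopsied |
|---|---|---|
| (a) | 0 | 0 |
| (b) | +13.3 | +13.3 |
| (c) | −8.9 | −8.9 |
| (d) | +5 | +10.8 |
| (e) | −8 | −14 |

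With a two-sided 5% test (also an assumption) and 60 biopsied, the chance of a significant difference that is purely ascertainment is about 47% in case (b) and 34% in case (e).

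**Step 4. Reading the table.** Incomplete coverage alone does no harm to the endpoint as written (a). Harm comes from selective receipt of surveillance biopsy (b, c), or from a numerator or denominator that departs from surveillance biopsies (d, e). The plan excludes none of these.

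**Step 5. Antibodies.** No figures are available. Fewer tests among controls would miss early or transient antibody and lower their rate. Tests ordered only on suspicion would raise the rate among those tested. The direction is open.

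**The case against.** The best reply is that the plan intends equal ascertainment. Its data list names both cohorts at the same months. Only the donor biopsy is qualified by availability, and only for-cause biopsies are worded as something a patient might or might not have had. The surveillance results carry no such caveat, which suggests that the authors expected to find them in control charts. This has weight: if the centre already had the programme, the bias may be small. It remains an inference, because a list of items to extract does not create tests and nothing states that the programme existed.

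The second reply is that the primary endpoint is restricted to surveillance biopsies. This also stands. A reader might infer from cases (d) and (e) that the plan as written produces a spurious difference. It does not say that for-cause biopsies enter the rate, nor that unbiopsied controls count as negative, and on the plainest reading with non-selective receipt the difference is zero. What survives is selective receipt, together with the plan's silence on the denominator.

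A reader might also infer that controls need only a transplant and immediate-release tacrolimus. They must also be African American and matched, and presumably adult and within the organ criteria. None of these bears on testing.

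**Conclusion.** The gap is real and worth closing before controls are selected. Control eligibility does not secure the tests on which both endpoints rest. If the centre did not run the same schedule throughout the control period, either rate can differ between cohorts because of ascertainment. If it did, the effect may be small.

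The documents give no coverage, no event rates and no number of controls, so neither size nor direction can be stated. The figures above illustrate mechanisms under assumed inputs and are not estimates for this study.

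Two stronger conclusions are tempting. A reader might infer that neither comparison can be read as a formulation effect. On this point that would follow only if coverage actually differed and was selective, which the documents do not show. A reader might also infer that the direction of any bias could never be established. The plan collects biopsy type and scheduled time, so coverage can be tabulated by cohort and the likely direction examined.

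**What to change.** 1. **Control selection.** Take as controls, or as the pool to match from, consecutive eligible recipients by transplant date from the most recent period in which the centre ran the same 3- and 12-month surveillance biopsies and the same scheduled antibody tests. State the dates. Do not select on having a 12-month biopsy, so that early losses stay in the cohort.
2. **Primary rate.** In both cohorts, count toxicity on surveillance biopsies within the same visit windows, with patients who had such a biopsy as the denominator. Report for-cause biopsies separately.
3. **Antibody rate.** Compare the cohorts only on tests within the same windows.
4. **Coverage.** Report the number biopsied and the number tested at each scheduled time in each cohort. A biopsied-only denominator does not remove selection, and this table shows how much room is left for it.

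The change is a matter of wording and a date window. The price is a smaller pool of controls to match from. If the centre's records show no such period, it is better to learn that before the comparison is made.

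### Eligibility has no index date: an undated adverse-reaction exclusion, applied to completed charts, could remove immediate-release controls for post-transplant events while equivalent Envarsus patients stay enrolled

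*Combined protocol and SAP*

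**What the plan says.** **Envarsus cohort.** Study Type/Design says that "a prospective cohort will be started de novo on Envarsus at the time of renal transplantation", and the dosing section repeats that "Patients enrolled in the prospective arm of the study will be started on Envarsus XR". Treatment Overview places screening in the evaluation and wait-list clinics and before scheduled surgery. One hundred patients are to be consented.

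**Controls.** Patient Recruitment describes a matched retrospective cohort of African American recipients "who received renal transplant and were treated with immediate release tacrolimus". It gives no requirement that the drug was started at transplant, and no minimum exposure, calendar window, sampling rule, matching variables or matching ratio.

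**Eligibility.** Exclusion 4 reads "Adverse reaction to tacrolimus", undated and not confined to one cohort. Inclusion 3 reads "Previous adverse reaction or contraindication to the use of tacrolimus", which contradicts it.

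**Endpoint and follow-up.** "Primary endpoint is to determine the rate of calcineurin inhibitor toxicity as measured by surveillance kidney biopsies". Surveillance biopsies after transplant are at 3 and 12 months. Data are collected at time 0 and at 1, 3, 6 and 12 months in both cohorts.

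**Switching.** Potential Pitfalls and Contingencies says that if side effects are attributed to tacrolimus, "then the patient may have to be switched to another immunosuppression regimen". No section says how such a patient is analysed, and the data list has no item for the date or reason of a switch.

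**The concern.** The same criterion can behave differently in the two cohorts. A prospective patient passes exclusion 4 before surgery and is then enrolled, so a later reaction cannot undo entry. A control is assessed from a chart that may already contain the post-transplant course, so the same words can exclude that patient for something that happened after time 0. The loose definition by treatment leaves a second opening: an abstractor may keep only patients who stayed on immediate-release tacrolimus.

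If controls lost in this way have more toxicity on biopsy than the rest, the control rate is too low and the comparison is tilted against Envarsus, possibly hiding the benefit that the hypothesis predicts. Leaving Envarsus switchers out of the analysis would tilt it the other way if they too have above-average toxicity. The listed methods (chi-square, t-test, Kaplan-Meier) do not correct selection on events after baseline.

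**Working it through.** **1. The entry rules side by side**

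| | Envarsus | Immediate-release controls |
|---|---|---|
| Defined by | drug started at transplant | having been treated with the drug |
| When eligibility is judged | before surgery | not stated; from past records |
| Can a post-transplant reaction meet exclusion 4 at entry? | no | yes, on a literal reading |
| Rule for later switchers | none | none |

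**2. There is no figure of the plan to reproduce.** The protocol gives no expected rates, effect size or power. The number of controls, the alpha level and the sidedness are also unstated. Everything below is illustration.

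**3. Assumptions.** True toxicity *p* = 30% in both cohorts; 100 Envarsus patients (from the protocol) and 100 selected controls (assumed); chi-square test without continuity correction, two-sided 0.05. A share *s* of the eligible controls is lost, and their toxicity risk is *t*.

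Observed control rate = (*p* − *s·t*) / (1 − *s*)

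- *s* = 0.10, *t* = 0.40: (0.30 − 0.04)/0.90 = 28.9%
- *s* = 0.20, *t* = 0.40: (0.30 − 0.08)/0.80 = 27.5%
- *s* = 0.10, *t* = 0.60: (0.30 − 0.06)/0.90 = 26.7%
- *s* = 0.20, *t* = 0.60: (0.30 − 0.12)/0.80 = 22.5%

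The false rejection rate is found by exact enumeration of all pairs of binomial counts:

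| Risk *t* of those lost | 10% lost | 20% lost |
|---|---|---|
| 30% (average) | 5.1% | 5.1% |
| 40% | 5.4% | 6.8% |
| 60% | 8.2% | 22.4% |

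With average risk the formula returns 30% and there is no bias; the 5.1% is the test's own exact size. If those lost had below-average risk, the sign would reverse: *s* = 0.10, *t* = 0.20 gives (0.30 − 0.02)/0.90 = 31.1%.

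**4. Effect on a true benefit.** Suppose the true Envarsus rate is 13.7% (assumed; it gives 81.0% power against 30% with 100 per group). Lost controls are now not replaced, so 90 or 80 remain:

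| Risk *t* of those lost | 90 controls | 80 controls |
|---|---|---|
| 30% (smaller sample only) | 79.0% | 76.2% |
| 40% | 74.0% | 63.5% |
| 60% | 61.9% | 33.4% |

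The first row separates the loss from smaller numbers from the loss due to bias.

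**The case against.** The strongest reply is that this is an ambiguity and not a stated rule. Several parts of it stand.

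- **Nothing says switchers are removed.** Having been treated with a drug fits having ever started it at least as well as having stayed on it. The secondary endpoint uses the same verb for both groups, and the hypothesis also uses one verb for both. The wording contrast alone does not prove a different rule.
- **Nothing says outcomes guide the choice of controls.** A reader might infer this from the retrospective source, or from the design statement, "This is a case control study where a prospective cohort will be started de novo on Envarsus". The documents do not support it. Outcomes may already exist in the charts, but no selection on them is described. The case-control label is a misnomer for groups formed by drug, and it changes no selection rule.
- **Both cohorts share a time 0 and one follow-up schedule**, and inclusion 3 refers to a previous reaction, which suggests that pre-transplant history was meant. The plan does not say that controls are judged at a different time.
- **No section links clinical reactions to biopsy toxicity.** The adverse events described in the Introduction are neurologic. A reader might treat exclusion 4 as almost the endpoint itself; the documents do not establish that, and the bias depends on it.

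What does not fall is the asymmetry. Applied literally, an undated exclusion can remove a control for a post-transplant event and cannot do so at pre-transplant screening. The contradiction between inclusion 3 and exclusion 4 leaves an abstractor without a usable rule, and no section closes the gap.

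**Conclusion.** The point holds as an unclosed gap that could bias the primary comparison, not as a bias shown to be operating. The direction is downward for the control rate only if the controls lost have above-average biopsy toxicity. The size cannot be known from the documents. Under the assumptions above, false rejection runs from the nominal level to about 22%, and the upper end needs both a 20% loss and a 60% risk among those lost. At 40% risk the distortion is small. The change is worth making because the comparison carries the only primary hypothesis and, without a record of switches, the problem could not be measured afterwards.

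**What to change.** 1. Apply every eligibility criterion in both cohorts using only information known on the day of transplant. Reconcile inclusion 3 with exclusion 4; which should stand is for the sponsor to decide.
2. Select controls from consecutive African American adult recipients started on immediate-release tacrolimus at transplant within a stated calendar window, matched on time-0 variables without reference to biopsy, antibody or other post-transplant results.
3. Analyse every patient by starting formulation, regardless of later switch.
4. Record the date and reason of each switch, and missing biopsies, in both cohorts, and report them descriptively by cohort. Do not censor at switch: such censoring is likely to be informative, could bring the selection back, and does not suit a binary biopsy endpoint.
5. Describe the design as a prospective cohort with matched historical controls.

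The cost is protocol wording and one extra chart field for switches. The one statistical downside is that keeping switchers dilutes the on-drug contrast.
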